8.2.5 Procedures for Recording of Adverse Events

8.2.5.1 Diagnosis versus Signs and Symptoms

A diagnosis (if known) should be recorded for that Adverse Event rather than individual signs and symptoms (e.g., record only liver failure or hepatitis rather than jaundice and elevated transaminases).

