8.2.6 Adverse Events of Special Interest

Adverse events of Special Interest are defined as pre-specified AEs, serious and non-serious, under ongoing monitoring by the Sponsor.

No specific reporting timelines or other activities are required by the Investigator in addition to the normal AE reporting practices as described in the above sections for the followings AE of special interest:

- Supraventricular arrhythmias
- Sepsis, septic shock, grade ≥ 3 lung infection (pneumonia)
- Any infection leading to death
- Grade ≥ 3 anemia, neutropenia, febrile neutropenia and thrombocytopenia
- Grade ≥ 3 haemorrhage

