Each TEAE is collected in the eCRF by recording one initial record and one record for each change in seriousness and/or severity within the same occurrence of the event. A summary record will be derived aimed at being used for the production of the summary tables, while individual records will only be listed.

The summary record will pick-up among the collected records relevant to the same event (it is allowed to collect one field from one record and another field from another record) the maximum seriousness and the maximum severity. Actions taken will be picked up from all the records in order to keep all the actions taken with the event. The outcome will be picked up from the last record in time-sequential order. The relationship will be reconciled during data cleaning, so it will be the same in all of the records related to the same event at time of analysis.

As MRD (positive/negative) will be obtained together with the other data related to MRD analyses from the external lab, CR_{MRD} will be derived in the CDISC datasets from CR and MRD results.

Adverse events of special interest (as described in the study protocol) will be retrieved according to the following rules reported in the table:

AESI	MedDRA SMQ (v.20.0)	MedDRA PT (v. 20.0)	Comments
QTc prolongation	Torsade de Pontes/QT prolongation (SMQ) - NARROW	n/a	
Supraventricular arrhythmias	Supraventricular tachyarrhythmias (SMQ) - NARROW	n/a	
Sepsis, septic shock, grade ≥ 3 lung infection (pneumonia), any infection leading to death	Toxic-septic shock conditions (SMQ) - NARROW	1.Any PT that includes the word sepsis 2.Exact match to the PT pneumonia or lung infection	Pneumonia only if grade ≥ 3

Grade ≥ 3 anemia, neutropenia, febrile neutropenia and thrombocytopenia	n/a	
1.Any PT that includes the word anaemia.
 
2.Exact match to any of the following PTs:
 
Haemoglobin decreased Band neutrophil count decreased Band neutrophil percentage decreased Febrile neutropenia Granulocyte count decreased Granulocytopenia Neutropenia Neutropenic infection Neutropenic sepsis Neutropenic colitis Neutrophil count decreased Neutrophil percentage decreased Platelet count decreased Platelet production decreased Thrombocytopenia Febrile bone marrow aplasia
	All listed PTs only if grade ≥ 3
Grade ≥ 3 haemorrhage	n/a	Any PT that includes the word haemorrhage or haematoma or bleeding	All listed PTs only if grade ≥ 3

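### The SAP's word search for the Grade ≥ 3 haemorrhage AESI is narrower than the event the protocol defines, so severe bleeds coded to terms without those words drop out of the AESI outputs

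*SAP*

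**What the plan says.** Protocol 8.2.6 lists "Grade ≥ 3 haemorrhage" among the AESIs and attaches no condition on site, cause or wording.

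SAP 6.4 states that its table carries out the protocol's definitions: "Adverse events of special interest (as described in the study protocol) will be retrieved according to the following rules reported in the table". In the haemorrhage row the SMQ cell is marked not applicable, the PT cell reads "Any PT that includes the word haemorrhage or haematoma or bleeding", and the comment cell adds the grade filter, "All listed PTs only if grade ≥ 3". The row has no second rule and no medical-review step.

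The other four rows use more than a word search:
- QTc prolongation and supraventricular arrhythmia each use an SMQ, for example "Supraventricular tachyarrhythmias (SMQ) - NARROW".
- The sepsis and infection row uses "Toxic-septic shock conditions (SMQ) - NARROW" together with PT rules.
- The cytopenia row has no SMQ, but adds to its word match a list headed "Exact match to any of the following PTs", which names 16 terms.

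The retrieved terms feed the two AESI lines of the overview summary and the AESI tables in SAP 9.2.2 (by worst grade, by frequency, and restricted to drug-related events), the by-cycle versions in SAP 9.2.7, and Listing F13 in SAP 14.

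**The concern.** Many bleeding diagnoses are named by site or sign and contain none of the three search words. A Grade 3 nosebleed coded to epistaxis is a severe haemorrhage in the protocol's sense, but the SAP rule would not flag it as one.

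Bleeding is a relevant risk in this trial. Protocol 4.2.2.2 names haemorrhage as a feature of myeloid malignancies and urges caution with anticoagulant and antiplatelet drugs. Protocol 4.5 says that both drugs cause myelosuppression, including thrombocytopenia. A reader of the safety report who wants the number of patients with a severe bleed in each arm will go to the haemorrhage AESI row. If that row counts a narrower event under the protocol's label, the reader has no signal that terms are missing.

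**Working it through.** The documents state no figure for this item, so there is nothing to reproduce. The check is to apply the rule as written and trace which outputs it affects.

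**Step 1. Apply the rule.** Match 'haemorrhage', 'haematoma' or 'bleeding' anywhere in the PT, ignoring case.

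| Term | Retrieved? |
|---|---|
| Epistaxis | No |
| Melaena | No |
| Haematemesis | No |
| Haemoptysis | No |
| Haematuria | No |
| Haematochezia | No |
| Haemorrhagic stroke | No |
| Gastrointestinal haemorrhage | Yes |
| Cerebral haemorrhage | Yes |
| Subdural haematoma | Yes |
| Gingival bleeding | Yes |

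'Haemorrhagic' fails because it ends in -gic and does not contain the string 'haemorrhage'. All seven terms marked No describe bleeding, and nothing else in the row picks them up. That bleeds are coded to these terms is an assumption about MedDRA v20.0, which the SAP uses but does not reproduce.

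**Step 2. Compare the rows.** There are five AESI rows. Three use an SMQ and one adds a list of exact terms to its word search. Haemorrhage is the only row that rests on a word search alone.

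**Step 3. Trace the missed events.** A missed Grade ≥ 3 bleed that is treatment-emergent still appears by arm under its own PT in the TEAE tables by worst grade and in the Grade ≥ 3 table (SAP 9.2.2). Where applicable it also appears in the tables of related events, of events leading to dose change or discontinuation (9.2.3), of serious events (9.2.4) and of fatal events (9.2.5), and in the full listing (9.2). These tables are organised by organ class and PT. The number of patients with at least one severe bleed cannot be obtained by adding PT rows, because one patient may contribute to several.

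**Step 4. Size.** Let N be the patients per arm, r the true proportion with at least one Grade ≥ 3 bleed, and f the share of those patients with no Grade ≥ 3 bleed under a matching term. The AESI row then shows N × r × (1 − f) patients. N = 250 is the planning maximum (500 patients randomised 1:1). The documents give neither r nor f, so the values below are assumptions for illustration only.

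| r | True count per arm | f = 0 | f = 0.1 | f = 0.5 |
|---|---|---|---|---|
| 5% | 250 × 0.05 = 12.5 | 12.5 | 12.5 × 0.9 = 11.25 | 12.5 × 0.5 = 6.25 |
| 10% | 250 × 0.10 = 25 | 25 | 25 × 0.9 = 22.5 | 25 × 0.5 = 12.5 |

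Here f is a share of patients, not of events. A patient with both an epistaxis and a gastrointestinal haemorrhage at Grade ≥ 3 is still counted, so the loss in patients can be much smaller than the share of bleeds missed.

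**The case against.** **The events are reported elsewhere.** This is right. A reader might infer that severe bleeding disappears from the safety report, and the documents do not support that: each event stays visible under its own term and grade. What is lost is the grouped patient count, and no other planned output supplies it.

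**Coding practice may rescue many of these bleeds.** Protocol 8.2.5.1 says that "A diagnosis (if known) should be recorded for that Adverse Event rather than individual signs and symptoms". Haematemesis, melaena and haemoptysis are often signs, and the recorded diagnosis may contain 'haemorrhage'. This stands in part. The instruction applies only where a diagnosis is known, and it does not help when the site name is itself the diagnosis. Protocol 8.2.5.3 also pulls the other way: when an abnormal laboratory value comes with signs or symptoms, it is the sign or symptom that is to be reported.

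**Nothing points to a difference between arms.** A reader might infer that the rule conceals extra bleeding caused by pracinostat, citing the 46% rate of Grade ≥ 3 thrombocytopenia in Protocol 1.3. That figure is for the combination in a single-arm study and does not show what pracinostat adds. Protocol 3.3.3 describes the safety profiles as similar, and Protocol 4.5 says myelosuppression is about as frequent with either drug. The documents give no basis for expecting the missed bleeds to fall unevenly.

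**The stakes are limited.** The AESI outputs are descriptive, carry no test or alpha, and Protocol 8.2.6 asks nothing extra of investigators for these events. This is accepted, and no efficacy conclusion changes.

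**Conclusion.** The point holds as a mismatch between the two documents. The protocol defines any Grade ≥ 3 haemorrhage as an AESI, and the SAP retrieves only the part whose PT contains one of three words. This is a stated rule that gives the wrong event set, not a detail left for later. The AESI overview lines, the AESI tables (overall, related and by cycle) and Listing F13 are affected.

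The size of the under-count cannot be found from the documents. It is zero if every patient with a severe bleed also has one under a matching term, and the counts in the working are illustrations only. It would be going too far to say that severe bleeding is hidden, that the difference between arms is understated, or that the result favours pracinostat. The conclusion rests on a literal reading of the rule and on MedDRA v20.0 coding bleeds to terms such as those tested.

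**What to change.** In the haemorrhage row of SAP 6.4, supplement the word match with a haemorrhage SMQ from the MedDRA version already in use. Alternatively, add an explicit list of bleeding PTs in the manner of the cytopenia row. Keep the Grade ≥ 3 filter.

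SAP 11 records that version 5 followed the unblinding of the interim results, so the change can no longer be presented as made before any unblinding. Therefore:
- have the term list fixed by reviewers without access to treatment-level adverse event data;
- label the change as made after the interim unblinding;
- report the existing word-match count beside the broader one, so that the effect of the change is visible.

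The cost is one table cell and a rerun of the AESI tables and Listing F13. There will be a few more terms to review, and bleeding counts may rise in both arms.

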7 STUDY POPULATION

7.1 PATIENT DISPOSITION

Patient disposition will be presented for all screened patients. The composition of the analysis sets and strata and those who were screened, failed screening, were randomized, treated, randomized and not treated, are still ongoing, discontinued from the study treatment, entered in long-term follow-up and those who discontinued from the long-term follow-up will be summarized by treatment group and overall. Reasons for discontinuation from study treatment will be presented with frequencies and percentages for all categories: adverse event, progressive disease, death, lost to follow-up, non-compliance by subject, physician decision, pregnancy, protocol deviation, withdrawal by patient, other. Reason for discontinuation will be also reported by cycle. Number of cycles performed by patients (by category or as median number) will be reported.

Also reasons for discontinuation from long-term follow-up will be presented with frequencies and percentages for all relevant categories (lost to follow-up, death, withdrawal by patient, physician decision, study terminated by sponsor, other).

Additionally, the number of patients where randomization code was broken by investigator together with the reason for breaking the code will be provided.

7.2 DEMOGRAPHIC CHARACTERISTICS

Demographic and baseline characteristic data will be summarized with descriptive statistics for age, gender, self-reported race/ethnicity, baseline height, baseline weight, cytogenetic risk category (central lab results and results used for randomization), and ECOG grade at baseline (used at randomization and at Cycle 1 Day 1), smoking status at baseline and descriptive statistics of numbers of cigarettes/cigars/pipes for patients who are current smokers. Additionally serology (HIV, HBV, HCV) examination at baseline will be presented. These summaries will be done for ITT, ITT-2 and SAF sets.

Baseline AML Characteristics

The following data will be summarized:

- Bone marrow blast count at diagnosis/screening ($\geq 20\%$ and $\leq 30\%$; and $>30\%$ categories)
- De-novo AML (defined as absence of antecedent hematological disorders and therapy-related myeloid neoplasms)
- WHO 2016 AML Classification:
 - AML with recurrent genetic abnormalities (Y/N) and types (absolute and relative frequencies)
 - AML with myelodysplasia related changes (Y/N)
 - Therapy related myeloid neoplasms (Y/N) and types (absolute and relative frequencies)
 - AML not otherwise specified (Y/N) and types (absolute and relative frequencies)
- Extramedullary disease
- Classic cytogenetic analysis results

-
- Cytogenetic FISH results (if done)
 - Molecular analysis results (if done)
 - Prior hydroxyurea for cytoreduction (Y/N obtained from the prior/concomitant medication form by considering the ATC code L01XX (hydroxyurea))
 - Prior cycle with hypomethylating agents (Y/N obtained from the prior/concomitant medication form by considering the ATC code L01BC (azacitidine and decitabine)).

These summaries will be done for ITT, ITT-2, and SAF sets. A listing of patients who received hydroxyurea and hypomethylating agents, including details on the specific drugs, will be produced.

7.3 PRIOR AND CONCOMITANT MEDICATIONS

Concomitant medications will be coded with the World Health Organization (WHO) drug dictionary (B3 Enhanced format dated 01 March 2018). Version used at the start of the study will be used until the end of the study. Concomitant medications will be summarized with frequencies and percentages by drug Anatomical Therapeutic Chemical (ATC) Classification System (level 4), generic name, and treatment group. A data listing will be included that shows all medications by generic name and verbatim name. Prior anti-cancer therapies will be listed by drug (ATC level 4), generic name, and treatment group. Pre-treatment medications will be excluded from the summary table but included in the listing of all prior/concomitant medications. New anticancer therapy started during or after treatment period will be reported in a summary table (ATC level 4 and generic name), and will be listed. These summaries will be based upon the ITT set.

7.4 MEDICAL HISTORY AND PHYSICAL EXAMINATION

Medical history (non AML specific, coded with MedDRA version 20.0) will be summarized with descriptive statistics (frequencies and percentages) by medical history code and treatment group. A comprehensive data listing will also be included. These summaries will be based upon the ITT set.

AML history

Specific hematological disorders prior to study start could be entered into the CRF. The frequency and percentage of any prior hematologic disorder, the type of the hematological disorder, time from initial diagnosis of antecedent hematologic disorder to initial diagnosis of AML (months), and anti-cancer therapies will be presented in a summary table for the ITT, ITT-2, and SAF sets.

Physical examination

Baseline examinations will be presented as summary table by treatment group. The baseline examination is defined as the examination done in the screening period. Examinations performed during study follow-up will be listed. These summaries will be based upon the ITT set.

7.5 INCLUSION/EXCLUSION CRITERIA

Inclusion and exclusion criteria failures will be summarized for the screened patients by treatment group and overall in a table and also shown in a data listing.

7.6 PROTOCOL DEVIATIONS

Protocol deviations will be summarized by treatment group and category for the ITT set. Deviations will be classified as major or minor, with major deviations resulting in exclusion from the Per Protocol set. Deviations referring to assessment of the disease might have impact also on the inclusion into the EE sets. The final decision whether a protocol deviation is major or minor and the assignment to the analysis sets is made at the BDRM.

A listing of all deviations will also be included. Included in the listing will be those protocol deviations coming from the PD tracker generated during study by the CRAs and those protocol deviations coming from the specific listings generated for the BDRM by programming.

For Covid19 related protocol deviations a separate listing will be provided.

7.7 UNBLINDING OF TREATMENT INFORMATION

Patient's treatment information can be unblinded by investigator or sponsor's drug-safety department for regulatory communications. Data of patients unblinded by sponsor will be used as no impact on the conduct of the study is expected. Data obtained before the unblinding by investigator will be used in the analyses without restrictions. Overall survival data will be used without any restrictions for unblinded patients. Individual cases will be examined at the BDRM to evaluate whether a potential impact of unblinding on efficacy is to be considered.

7.8 CENSORING RULES FOR TIME TO EVENT ANALYSES

The rules for censoring of time to event variables are described in the following. Incomplete dates for the new AML therapies which are used as censoring variable in some of the analyses will be imputed using the rules described in chapter 6.1.1 of the SAP. The imputations are done prior to the use of the new AML therapies as censoring variables, so that only complete dates are used for the censoring rules.

Rules for the use of new AML therapies as censoring variable in time to event analyses:

- Treatment with HDAC is regarded as new AML therapy
- G-CSF is not regarded as new AML therapy and therefore the treatment with G-CSF is not regarded as censoring variable.
- Treatment with decitabine, Azacitidine or hydroxyurea given only for up to 3 days are not regarded as new AML therapy and therefore not regarded as censoring variables
- Treatment with Methotrexate for the treatment of Crohn's disease is not regarded as new AML therapy and therefore not regarded as censoring variable.
- A new AML therapy that started and ended before Day15 of Cycle1 of the treatment phase of the study are not regarded as censoring variable in the time to event analyses.

-
- If a new AML therapy started before Day15 of Cycle1 of the treatment phase of the study and ended at or after Day15 of Cycle1 then the censoring starts at Day15 of Cycle1.
 - If a new AML therapy started at or after Day15 of Cycle1 of the treatment phase of the study then the new AML start date is taken as censoring timepoint.
 - If more than one new AML therapies are documented for one patient then only the start of the first therapy is used as censoring timepoint.

According to protocol only hydroxycarbamide (hydroxyurea) is allowed during the first 14 days of cycle 1; the rule for this treatment was enlarged to 28 days, using a pragmatic approach.

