3.4.2 Exclusion Criteria

Patients who meet any of the following criteria will be excluded from study entry:

1. Able to receive intensive induction chemotherapy
2. AML-associated inv(16)/t(16;16)/del(16q), t(15;17) (i.e., promyelocytic leukemia) with/without secondary aberrations; t(8;21) lacking del(9q) or lacking complex karyotypes
3. Presence of an active malignant disease within the last 12 months, with the exception of adequately treated cervical cancer in-situ, non-melanoma skin cancer and superficial bladder tumors (Ta [non-invasive tumor], Tis [carcinoma in situ] and T1 [tumor invades lamina propria]). Other malignancies may be considered after consultation with the Medical Monitor
4. Life-threatening illnesses other than AML, uncontrolled medical conditions or organ system dysfunction that, in the Investigator's opinion, could compromise the patient's safety or put the study outcomes at risk
5. Uncontrolled arrhythmias; any Class 3-4 cardiac diseases as defined by the New York Heart Association (NYHA) functional classification ([Appendix E](#))
6. Evidence of central nervous system (CNS) involvement
7. Previous therapy for AML except for the following, which are allowed:

- a. Hydroxyurea for cytoreduction
 - b. One course of hypomethylating agent therapy (i.e., up to 7 doses of azacitidine or 3-5 days of decitabine) within 30 days prior to enrollment (Day1)
8. Use of experimental drugs \leq 30 days prior to screening
 9. Received any prior HDAC inhibitor therapy
 10. Received prior treatment with a hypomethylating agent, except as allowed in Exclusion Criterion 7.b
 11. Known hypersensitivity to any components of pracinostat, AZA, or mannitol
 12. Human immunodeficiency virus (HIV) infection or an active and uncontrolled infection with hepatitis C virus (HCV) or hepatitis B virus (HBV)
 13. Gastrointestinal (GI) tract disease that causes an inability to take oral medication, malabsorption syndrome, or a requirement for IV alimentation; prior surgical procedures affecting absorption; or uncontrolled inflammatory GI disease (e.g., Crohn's disease, ulcerative colitis)

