4.7.3 Prohibited Concomitant Medications

The following treatments and/or medications are prohibited while on study:

- Any other investigational product taken within 4 weeks prior to Day 1 of Cycle 1 and/or through the entire study treatment period is not allowed. For this purpose "Other investigational product" has to be intended as any agents tested in clinical trials, even those which are tested for indications that are already approved.

- Anticancer agents. If such agents are required, then the patient must discontinue study treatment prior to receiving the anti-cancer therapy and disease progression should be documented. For patients at Cycles 1 through 6, it is recommended to contact the Medical Monitor prior to study treatment discontinuation. Every effort should be made to complete the End of Study Treatment visit **prior** to the patient starting any AML treatment regimen other than pracinostat/placebo + AZA.
- Hydroxyurea is allowed until Cycle 1, Days 1-14, to reduce WBC count to <30,000 μ L prior to Day 1. After Cycle 1, Day 14, hydroxyurea is prohibited.
- HDAC inhibitors.
- Medications with a known risk of prolonging the QT interval and/or causing Torsades de Pointes. ([Appendix I](#)).
- Herbal products are not allowed throughout the study. Subjects should stop using these prior to the first dose of study treatment.

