8 EFFICACY ANALYSES

In general, efficacy analyses will be performed on the ITT set (or the ITT-2 set).

Interceding therapies are defined as new treatment for AML including salvage treatments and hematopoietic stem cell transplantation (HSCT).

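### SAP 7.8 exempts a 3-day decitabine course at any time, and any AML drug finished before Cycle 1 Day 15, from the new-therapy censoring rules

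*SAP*

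**What the plan says.** SAP 7.8 lists which treatments count as new AML therapy and which act as censoring points.

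- **3-day rule:** "Treatment with decitabine, Azacitidine or hydroxyurea given only for up to 3 days are not regarded as new AML therapy". No calendar limit is given, and the text does not say whether the 3 days are per course or in total.
- **Day 15 rule:** "A new AML therapy that started and ended before Day15 of Cycle1 of the treatment phase of the study are not regarded as censoring variable". No drug is named. A companion bullet moves the censoring date to Day 15 when the therapy starts before Day 15 and ends on or after it.
- **Closing sentence:** "According to protocol only hydroxycarbamide (hydroxyurea) is allowed during the first 14 days of cycle 1"; it then adds that "the rule for this treatment was enlarged to 28 days, using a pragmatic approach". The 28-day figure appears in none of the bullets.

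SAP 8 links this list to the response endpoints: "Interceding therapies are defined as new treatment for AML including salvage treatments and hematopoietic stem cell transplantation (HSCT").

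On the protocol side, exclusion criterion 7.b (section 3.4.2) allows "One course of hypomethylating agent therapy (i.e., up to 7 doses of azacitidine or 3-5 days of decitabine") before enrolment. Protocol 4.7.3 prohibits other anticancer agents on study: "If such agents are required, then the patient must discontinue study treatment prior to receiving the anti-cancer therapy". Protocol 9.5 treats a response that follows an interceding therapy as not evaluable.

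**The concern.** A 3-day decitabine course meets the lower limit of what the protocol itself calls a course, yet the SAP scores it as no therapy, however late it is given. The Day 15 rule has the same weakness from another side. The reason given in the section concerns hydroxyurea alone, but the rule excuses every AML drug.

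Censoring at new therapy is meant to separate what happened on the randomised treatment from what happened after something else was given. Where it is skipped, later remission time or survival is counted as if no other treatment had intervened. SAP 13 makes censoring at new therapy part of the main analysis of duration of CR and cCR, and the defining feature of one sensitivity analysis each for OS, RFS and PFS.

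**Working it through.** **1. One patient, two classifications.** Take a patient in CR who stops study treatment before relapse.

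- Four days of decitabine: duration of CR is censored at the start of decitabine (SAP 8.3).
- Three days of decitabine: no censoring. Time runs on to relapse or to the last adequate assessment, and long-term follow-up still collects progression every 3 months (Protocol 5.2).

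A responder who had already relapsed before decitabine is not affected.

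**2. Day 15 rule.** A patient who leaves study treatment in week 1 and completes another regimen by Day 14 is not censored at all. If the regimen ends on Day 15 or later, censoring falls on Day 15 and not at its start, a delay of at most 14 days (15 − 1).

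**3. Which analyses each rule reaches.**

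| Analysis | 3-day decitabine rule | Day 15 rule |
|---|---|---|
| Primary OS (SAP 8.1) | No: not censored at new therapy | No |
| Main RFS and PFS (SAP 8.3) | No: not censored at new therapy | No |
| OS sensitivity (SAP 8.1.2), PFS sensitivity (SAP 8.3) | Yes | Yes |
| RFS sensitivity (SAP 8.3) | Yes | No: the set admits only CR/CRi reached without interceding therapy |
| Duration of CR and cCR, main (SAP 8.3) | Yes | No: same restriction on the set |
| CR, MRD-negative CR, CRc and cCR rates; time to CR | Possible, if the rule also defines interceding therapy | No CR is credited: the regimen is still new AML therapy |

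**4. How much data the response route has.** Response marrows are scheduled at Days 21 to 26 of even cycles (Protocol 5.1.11). The End of Treatment visit lists none (5.1.14), and long-term follow-up requires one only when progression is suspected (5.2). A first CR after stopping treatment and taking decitabine would therefore seldom be recorded.

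**5. Scale for the CR rate.** Inputs: 20% placebo CR rate and a difference of 0.13 (SAP 5.5); a maximum of 500 patients randomised 1:1 (Protocol 3.1), so 250 per arm.

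Reproducing the SAP's power of 0.91 at one-sided 0.025:
- Pooled rate = (0.20 + 0.33)/2 = 0.265; null SE = √(2 × 0.265 × 0.735/250) = 0.0395
- Alternative SE = √((0.20 × 0.80 + 0.33 × 0.67)/250) = 0.0390
- Power = Φ((0.13 − 1.960 × 0.0395)/0.0390) = 0.911, which agrees.

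One patient is 1/250 = 0.4 points. At the final secondary level of 0.023 (SAP 5.5) the smallest significant difference is about 1.995 × √((0.20 × 0.80 + 0.28 × 0.72)/250) = 1.995 × 0.038 = 7.6 points.

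The documents give no frequency. As an assumption, 2 to 5 patients in one arm, all scored as CR, would shift its rate by 0.8 to 2.0 points. The next table uses 1 and 2 points at one-sided 0.025.

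| Where the extra CRs fall | 1 point | 2 points |
|---|---|---|
| Placebo arm only: power | 0.86 | 0.79 |
| Both arms equally: power | 0.905 | 0.899 |
| Active arm only, true rates both 20%: rejection rate | 0.046 | 0.079 |

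Given step 4, these lie towards the unfavourable end. The 390 events, the significance levels and the stated power figures do not depend on SAP 7.8.

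**The case against.** **The Day 15 bullets probably had permitted use in mind.** They match the protocol's Day 14 limit for hydroxyurea, and the section's closing sentence speaks of that drug. This is plausible, but the bullets name no drug and a programmer would apply them to all.

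**The protocol's course definition is an eligibility allowance.** It admits patients after one such course and still attributes their response to the randomised arm. That is fair for doses before enrolment, and SAP 5.2 sends screening-period azacitidine or decitabine cycles to the blind data review meeting. Neither provision covers decitabine given later.

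**The 3-day bullet sits under a heading about censoring.** Its reach into the CR rate is therefore inferred. This stands: the wording and SAP 8 permit that reading but do not state it.

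**Azacitidine is a weak example.** Three days is under half of a 7-dose course, and azacitidine is the background drug in both arms. This also stands, and the point rests on decitabine.

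**The stakes are low and partly covered.** Duration of response is exploratory. New therapy is tabulated and listed (SAP 7.3 and 14). Balance between arms of patients with subsequent therapy is assessed, and further OS sensitivity analyses may be added (SAP 8.1.2). This limits the importance but does not correct the flag.

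**A stronger reading is tempting.** A reader might infer that a CR following a regimen exempted by the Day 15 rule is an event in time to CR but void in the CR rate. The documents do not support this. SAP 8.3 also requires the CR in time to CR to occur without interceding therapy, and that regimen remains new AML therapy.

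**Conclusion.** The point holds as a definitional fault of limited reach. Following SAP 7.8 literally gives censoring that does not serve its purpose in the main duration of CR and cCR analyses (3-day rule), in the OS and PFS new-therapy sensitivity analyses (both rules) and in the RFS one (3-day rule). The section is also inconsistent within itself on Day 15 against 28 days.

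A reader might go further and conclude that outcomes after other AML treatment are credited to the randomised arm throughout, including in the CR rate as first secondary endpoint. The documents do not carry that far. The CR-rate route depends on an inferred definition and on responses that the visit schedule would seldom capture.

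Neither frequency nor direction of bias can be derived. The 0.8 to 2.0 point shift assumes affected patients in one arm only, all scored as CR, and remains well below the 7.6 points needed for significance.

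**What to change.** In SAP 7.8:

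- limit the 3-day exemption for decitabine to doses given before Cycle 1 Day 1;
- restrict both Day 15 bullets to hydroxyurea, and reconcile them with the closing 28-day sentence;
- state that the same list defines interceding therapies in SAP 8.2 and 8.3.

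The cost is a few lines of text and a re-run of the new-AML-therapy flag. The downside is a few more censored times or voided responses. SAP 11 places this version after the interim results were unblinded, so results under the present and the revised flag should be shown side by side.
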